Objective: The goal of this study is to compare the clinical outcomes of DBS electrodes placed using intraoperative CT and frameless stereotaxis with those placed using MER and frame-based stereotaxis.

Design: The proposed study will be a prospective non-interventional data collection study.

Setting and Subjects: Subjects for this study will be idiopathic Parkinson's disease patients identified from the Oregon Health & Science University movement disorder clinic as candidates for deep brain stimulation therapy. We will also enroll patients referred by community neurologists to OHSU for deep brain stimulation therapy for idiopathic Parkinson's disease. These patients will be recruited in the OHSU movement disorder clinic during their evaluation for the deep brain stimulation procedure. Enrollment will continue until fifty subjects meeting inclusion and exclusion criteria have been implanted with electrodes using frameless stereotaxis and intraoperative CT. Data regarding quality of life, motor control, and amount of time during the day without levodopa-associated side effects will be collected pre-operatively and post-operatively. This data will be compared to historical controls who have been implanted with DBS electrodes using MER and frame-based stereotaxis. This data will be obtained from consulting the Veterans Affairs cooperative study entitled, "Bilateral Deep Brain Stimulation vs Best Medical Therapy for Patients with Advanced Parkinson Disease" published in JAMA in 2009 (5).

All surgical procedures will involve only Federal Drug Administration (FDA) approved stereotactic equipment, used in the manner for which they have been approved. All clinic procedures are standard of care for movement disorders patients in the deep brain stimulation program.

Intervention: This study will be a non-interventional data collection study.

Measurements: Data regarding patient age, diagnosis, intracranial target, complications, Unified Parkinson's Disease Rating Scale (UPDRS) Part 2 (activities of daily living), UPDRS Part 3 (motor examination), Parkinson's Disease Quality of life (PDQ-39), 3 day motor diary, and neuropsychological evaluation.

Analysis: The patients will be examined prior to DBS placement both on and off dopaminergic medications. All patients will receive their initial programming optimization visit approximately 30 days after electrode implant. The timing of further clinic visits for continued stimulator optimization will be up to the discretion of the DBS neurology provider and the patient. All patients will present for a 6 month visit following electrode placement. This visit will include the following procedures:

- UPDRS Part 2
- UPDRS Part 3
- PDQ-39
- Review of motor symptom diary
- neuropsychiatric evaluation, including:
 - Beck Depression Inventory-II (BDI-II)
 - Mattis Dementia Rating Scale-Second Edition (DRS-2)
 - Wechsler Abbreviated Scale of Intelligence (WASI)

We will also obtain information regarding adverse events directly related to surgery, falls and length of hospital stay.

A. Specific Aims

The objective is to compare the clinical outcomes of patients who receive placement of DBS electrodes by intraoperative CT scanning and frameless stereotaxis with those placed using frame-based stereotaxis and MER mapping for target verification. The primary outcome measure is change in the motor section of the UPDRS in the OFF-levodopa state from pre-operative baseline to 6-month followup.

B. Background

Deep Brain Stimulation has become standard therapy for medically intractable Parkinson's disease, Essential Tremor, congenital and acquired dystonias, and is currently being investigated in the treatment of other common disorders. Class I evidence now supports its use in patients with advanced Parkinson's disease, in comparison to best medical therapy (1).

OHSU has been a pioneer in the development and use of DBS, and was the first center after Grenoble, France to perform DBS implantation. The original FDA Investigational Device Exemption studies supporting DBS were conducted at OHSU in 1990-91. Since then, OHSU was the first center to conduct a randomized prospective comparison study of subthalamic nucleus (STN) DBS v. globus Pallidus pars interna (GPi) DBS, the results of which have now largely been replicated in a multi-center protocol conducted by the US Department of Veterans Affairs and the National Institutes of Health (2).

Throughout the history of DBS implant procedures at OHSU, MER and mapping of target structures has been the gold standard. However, it is highly unlikely that *any* future study will ever provide Class I evidence that MER adds significant value to the DBS implant procedure (3). On the other hand, the best available evidence would indicate that MER does add risk to the DBS procedure; approximately 1% chance of hemorrhage per MER pass.

Prior to the routine use of advanced imaging in movement disorder surgery, MER provided the required degree of localization and verification of stereotactic target centers for movement disorder surgery. With the advent of advanced MRI and CT imaging, particularly intra-operative imaging, the argument for the continued use of MER during DBS implantation has been substantially weakened. (4)

In addition to the added risk of hemorrhage with MER there is also a presumed increase in discomfort for the patients during this procedure. With MER, the patient must remain awake for the entire procedure, including frame-placement, magnetic resonance imaging, surgical incision and drilling of the site of insertion, MER, and closure of the site. Patients must also withhold dopaminergic medications for a minimum of twelve hours prior to the procedure creating a significant degree of discomfort and anxiety.

With placement of DBS electrodes by intraoperative CT scanning and frameless stereotaxis, MRI is obtained prior to the procedure. The patient is then taken to the operating room for anesthesia, the head is placed in a frame, CT scan is obtained, pre-operative MRI and intra-operative CT images are merged, the navigation site is determined, and DBS is placed surgically.

Because the surgical targets have not changed, it is hypothesized that patient outcomes will be comparable to those seen using the traditional MER and frame-based surgery. Furthermore, it is believed that this procedure will prove to be the preferred technique both from a clinician stand point as well as the patient's as it addresses many concerns patients have regarding deep brain stimulation surgery.

C. Methods

1. Subjects

Fifty appropriate surgical candidates (Group 2), with Parkinson's disease implanted using an intraoperative CereTom 8-slice CT scanner (NeuroLogica Corporation, Danvers, MA), StealthStation® treatment guidance system, (Medtronic Surgical Navigation Technologies Minneapolis, MN), and using the NeXframe frameless system (Medtronic, Minneapolis, MN) will form the study group. Subjects will be identified through clinic visits and review of medical records. Informed consent will be conducted in person or through a recruitment cover letter for telephone consent. For telephone consenting, subjects will be given the opportunity to review the consent and discuss the study with the study team before they sign the consent or complete any study procedures. The information collected from these patients will be compared to the published data on 121 DBS patients who underwent implantation of electrodes via frame based stereotaxis and MER for the treatment of Parkinson's disease (Group 1). We will obtain de-identified data from the VA Cooperative study, "Bilateral Deep Brain Stimulation vs Best Medical Therapy for Patients With Advanced Parkinson Disease." (5) No medical records, source documents, or case report forms will need to be accessed to obtain the necessary values needed to compare the two groups. All procedures will involve only FDA approved stereotactic equipment, used in the manner for which they have been approved. Medtronic lead # 3387 will be used for all DBS implants.

a. Inclusion criteria

1. Idiopathic Parkinson's disease patients identified by OHSU movement disorders neurologists and community neurologists as deep brain stimulation surgical candidates who choose to undergo implantation of DBS electrodes using intraoperative computed tomography and frameless stereotaxis in the treatment of Parkinson's disease
 - a. Hoehn and Yahr stage 2 or greater while not taking medication
 - b. Responsive to levodopa

- c. Persistent disabling symptoms (eg motor fluctuations, dyskinesia) despite medication
- d. Experienced 3 or more hours per 24-hour period with poor motor function or symptom control
- 2. Surgical sites include subthalamic nucleus and globus Pallidus pars interna
- 3. Age > 18 years

b. Exclusion criteria

1. Subjects with atypical parkinsonism or parkinsons-plus syndrome
2. Subjects who have undergone implantation of DBS electrodes using MER and frame-based stereotaxis or computed tomography and frameless stereotaxis in the treatment of other movement disorders.
3. Other previous surgeries for Parkinson's disease
4. Age < 18 years
5. Surgical target site other than subthalamic nucleus or globus Pallidus pars interna
6. Subjects who choose to undergo MER and frame-based stereotaxis for the placement of electrodes.

2. Study procedures

As this is a non-interventional data collection study, we will obtain patient consent. We will then compare the study group of 50 patients with the historical cohorts in the following measures: UPDRS Parts 2, 3 and 4, change in PDQ-39, change in amount of time patient is experiencing Parkinson's Disease symptoms and/or side effects of treatment, and neuropsychiatric evaluation.

DBS settings will be optimized 30 (+/-3) days after electrode implantation. Further DBS programming optimization will be performed at 60 (+/-3) and 90 (+/-3) days post-implantation.

Studies	Screening	Baseline	DBS Implant	30 day post-implant	60 day post-implant	90 day post-implant	6 month follow-up
Informed consent	X						
Demographics	X						
History & Physical		X		X	X	X	X
UPDRS Part 2		X					X
UPDRS Part 3 (ON and OFF)		X					X
UPDRS Part 4		X					X
DBS programming				X	X	X	
PDQ-39		X					X
Motor Diary		X					X
Neuropsychiatric evaluation		X					X
Adverse Events			X	X	X	X	X
Medications		X	X	X	X	X	X

D. Data Analysis and Interpretation

(1) Experimental design.

The proposed study is a prospective data analysis to compare the clinical outcomes of DBS electrode placement using intraoperative CT and frameless stereotaxis versus an historical control of DBS electrode placement using MER with frame-based stereotaxis (5).

(2) Analysis.

The primary outcome will be a comparison of change in motor UPDRS (part 3) in the OFF medication/ON stimulation state at 6 months postoperatively between groups 1 and 2. Analysis will be based on the intent-to-treat principle. For patients without baseline data, follow-up data or both, the change score will be set to zero. The mean group change will be compared between treatment groups using a 2-sample t test.

Secondary outcomes will be a comparison between groups 1 and 2 in the change from baseline to 6 months in ON time without dyskinesia, PDQ-39, and UPDRS part 2. In addition, a comparison will be made between groups 1 and 2 in the change from baseline to 6 months in the Beck Depression Inventory-II (BDI-II), Mattis Dementia Rating Scale-Second Edition (DRS-2), and the Wechsler Abbreviated Scale of Intelligence (WASI) , using a 2-sample t test. The sample size and power calculations are 2-tailed with an α level of 0.05.

(3) Sample Size Calculations.

Data from historical control patients using MER and frame-based stereotaxy (5) will be compared with 50 patients who undergo DBS placement using frameless stereotaxis and intraoperative CT.

E. Human Subjects

1. *Risks to Subjects:* As this is a non-interventional data collection study, no additional risks will be posed to the patients involved in this study. The patients will be treated using accepted surgical techniques, such as planning and surgical execution and all steps will be carried out in the usual fashion of performing such procedures in the Department of Neurological Surgery at OHSU. All clinical outcome measures are standard of care in the movement disorders center for patients in the deep brain stimulation program. Patient confidentiality will be respected during information retrieval.
2. *Potential Benefits of the Proposed Research to the Subjects and Others:* This research project proposed here aims to drive a paradigm shift, from MER verification of stereotactic targets, to an entirely image-based anatomic targeting methodology. We would like to demonstrate non-inferiority of the image-based anatomic targeting method in terms of treatment of Parkinson's disease symptoms.

The implications of this shift are:

- A. Increased patient comfort
- B. Operative procedures will be faster.
- C. Operative procedures will be easier, absent the requirement for MER equipment, macroelectrodes and electrophysiologic expertise.
- D. Most operative procedures can be performed entirely under general anesthesia.
- E. If intraoperative imaging is used, anatomic verification of the electrode position can be established prior to the patient leaving the operating room.
- F. Intraoperative images are provided to the neurologist which can be used to help guide selection of optimal programming configurations.

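### Does the intent-to-treat label conflict with a Group 2 made up of fifty implanted patients?

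*Combined protocol and SAP*

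**What the plan says.** Four places define or count Group 2 by the procedure completed:

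- Summary, Setting and Subjects: "Enrollment will continue until fifty subjects meeting inclusion and exclusion criteria have been implanted with electrodes using frameless stereotaxis and intraoperative CT".
- C.1 Subjects: "Fifty appropriate surgical candidates (Group 2), with Parkinson's disease implanted using an intraoperative CereTom 8-slice CT scanner". The same sentence ends "using the NeXframe frameless system (Medtronic, Minneapolis, MN) will form the study group".
- C.2 Study procedures: "We will then compare the study group of 50 patients with the historical cohorts in the following measures".
- D(3) Sample Size Calculations: the historical data "will be compared with 50 patients who undergo DBS placement using frameless stereotaxis and intraoperative CT".

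D(2) Analysis then says "Analysis will be based on the intent-to-treat principle", and its next sentence is "For patients without baseline data, follow-up data or both, the change score will be set to zero".

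Eligibility is settled before surgery: inclusion criterion 1 takes candidates "who choose to undergo implantation of DBS electrodes using intraoperative computed tomography and frameless stereotaxis", and exclusion criterion 6 removes those who opt for MER with a frame. No sentence says how to count a patient whose CT/frameless procedure is abandoned, or converted to MER, after consent.

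**The concern.** Intent-to-treat normally means that patients are analysed by the treatment intended, whether or not it was completed. The schedule in C.2 puts consent at screening and the UPDRS at baseline, both before implantation. A patient can therefore be eligible, consented and assessed without becoming one of the fifty. Because accrual stops on a count of implanted patients, the next patient could take that place. The zero-change rule would then never reach the patient who was not implanted.

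The stake is the hope in E.2 of showing that image-based targeting is non-inferior. An abandoned procedure is a failure of the technique under study. If the plan's own rule would score such a patient zero, leaving that patient out makes the Group 2 mean more favourable than an analysis of everyone intended for the procedure.

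**Working it through.** **Which set is analysed.** C.1 says who forms the study group, C.2 compares that group, and D(3) repeats the count. The aim in section A concerns patients who receive the electrodes. The primary endpoint in D(2) is measured with stimulation on, which presupposes an implant. All of these point to the fifty implanted patients.

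**What the label can mean.** There is no random assignment to preserve, because the comparison is one cohort against historical controls. The sentence after the label deals only with missing baseline or follow-up scores. Read together, the two sentences keep all fifty patients in the comparison, with zero change where data are missing. On that reading C.1, C.2, D(2) and D(3) agree.

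**Whether the groups match.** C.1 describes Group 1 as 121 patients who had electrodes implanted with a frame and MER. Both groups are therefore described by the procedure received.

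**Inputs for size.** The documents give the group sizes, 121 and 50. They give no derivation of the 50 that could be reproduced, and no abandonment rate, mean change or SD. Assumed here: mean improvement *m* in implanted patients of 12 points (range 8 to 16), and a common SD of 12 (range 9 to 15).

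**Effect of leaving out *k* abandoned cases scored zero.** Shift in the Group 2 mean = *m* × *k* / (50 + *k*).

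| *k* | *m* = 8 | *m* = 12 | *m* = 16 |
|---|---|---|---|
| 1 | 8/51 = 0.16 | 12/51 = 0.24 | 16/51 = 0.31 |
| 3 | 24/53 = 0.45 | 36/53 = 0.68 | 48/53 = 0.91 |

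**Standard error of the group difference.** SE = SD × √(1/121 + 1/50) = 0.168 × SD, which is 1.51, 2.02 or 2.52 points at SD 9, 12 or 15.

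**Shift in SE units at *m* = 12.**

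| *k* | SD 9 | SD 12 | SD 15 |
|---|---|---|---|
| 1 | 0.16 | 0.12 | 0.09 |
| 3 | 0.45 | 0.34 | 0.27 |

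**Cases needed for a larger shift.** For a target shift *t* in points, *k* = 50*t* / (12 − *t*). At SD 12, half an SE (*t* = 1.01) needs *k* = 4.6 and one SE (*t* = 2.02) needs *k* = 10.1. The latter is about 10 abandoned among 60 attempted.

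**Converted cases.** These patients have leads and can have a 6-month score, so the zero-change rule need not apply. Including *k* of them with improvement *c* moves the mean by *k*(*c* − 12)/(50 + *k*). For *k* = 3 this is −0.34, 0 or +0.34 points at *c* = 6, 12 or 18. The direction cannot be known in advance.

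**The alternative set.** Suppose Group 2 were enlarged to 50 + *k* while Group 1 stayed implanted-only. Three zero scores would then lower the Group 2 mean by 0.68 points (*m* = 12) with nothing equivalent in Group 1. The groups would differ by definition rather than by technique.

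**The case for a change.** The strongest case for a change is that the label and the group do not fit under the usual meaning of intent-to-treat. The zero-change rule gives a score to patients already in the analysis but does not say who they are. If the rule is meant to reach abandoned cases, Group 2 is larger than the fifty in C.2 and D(3). If it is not, the label claims more than the analysis delivers. Exclusion criterion 6 does not help, since it concerns a patient's choice and not a conversion during surgery. A couple of sentences would settle this, and settling it before outcomes are known is more credible than doing so afterwards.

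Much of this stands: the label is loose, and the rule for abandoned and converted cases is unwritten. Two parts do not carry through. First, the accrual rule says when enrolment stops; that consented patients are replaced or dropped is an inference. Second, no benefit to the primary comparison is shown. If Group 1 is implanted-only, as C.1 describes it, the matching Group 2 set is the one the plan already uses and only the label is at issue. If Group 1 was formed in some other way, the documents do not show it, so they cannot support choosing a different set.

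**Conclusion.** No change to the plan follows. The plan identifies Group 2 as the fifty implanted patients, and the intent-to-treat sentence has a workable meaning alongside the missing-data rule. The historical group is described in the same terms, so no bias between the groups is shown. What remains is an imprecise label and an unstated rule for a situation that may not arise. An analyst would fill that gap by analysing the fifty and reporting any abandoned or converted cases beside them.

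The effect is nil if no procedure is abandoned. On the assumed 12-point improvement and SD of 12, it is 0.12 SE for one case and 0.34 SE for three. The conclusion rests on abandonment being uncommon, which the documents neither state nor contradict, and on C.1's description of Group 1 being accurate. About five abandoned cases would be needed to move the Group 2 mean by half a standard error, and about ten to move it by a whole one.

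### Placement technique is fully confounded with data source, and the planned t test makes no allowance for any other difference between the two series

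*Combined protocol and SAP*

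**What the plan says.** Section D(1) sets CT-guided frameless placement "versus an historical control of DBS electrode placement using MER with frame-based stereotaxis". The opening summary says the same of the outcome data: "This data will be compared to historical controls who have been implanted with DBS electrodes using MER and frame-based stereotaxis".

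- **Group 2.** Patients are recruited at the OHSU movement disorder clinic, and "Enrollment will continue until fifty subjects meeting inclusion and exclusion criteria have been implanted with electrodes using frameless stereotaxis and intraoperative CT".
- **Group 1.** Under C.1, the new data will be "compared to the published data on 121 DBS patients who underwent implantation of electrodes via frame based stereotaxis and MER". The source is a single cooperative study published in 2009. C.1 calls its data both published and de-identified, so it is unclear whether patient-level records will be available.
- **No MER patients at OHSU.** Exclusion 6 in C.1.b removes "Subjects who choose to undergo MER and frame-based stereotaxis for the placement of electrodes".
- **Analysis.** D(2) compares mean change in OFF-medication/ON-stimulation UPDRS part 3 at 6 months by a 2-sample t test; the sample-size paragraph refers to a two-tailed α of 0.05. No covariate adjustment, matching, weighting, between-series allowance or sensitivity analysis is planned.
- **Intended use.** Section B hypothesises comparable outcomes. E.2 speaks of showing non-inferiority and of shifting practice towards image-based targeting. No margin is given.

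**The concern.** The two groups differ in technique, and also in treating programme, calendar period, conditions of assessment and case mix. No patient in the data set breaks that link, because nobody has MER placement in the OHSU series and nobody has CT/frameless placement in the external one. The t test compares the observed difference with patient-level sampling error alone. It cannot tell a technique effect from any other difference between the series.

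This matters because of how the result will be used. If the OHSU series would have done better for reasons unrelated to technique, a truly worse placement method could look comparable. If it would have done worse, a sound method could look inferior. In either case the plan as written would credit the result to the placement method.

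**Working it through.** The plan states no SD, effect size, power or margin for the primary endpoint, so there is no figure of its own to reproduce. The check is in units of the patient-level SD of the change score.

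**Inputs from the documents:** n₂ = 50 (summary, C.1, D(3)); n₁ = 121 (C.1); two-sided α = 0.05 (D(2)).

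**Inputs assumed:** a fixed net series shift b in mean change, unrelated to technique, of 0.1, 0.2 or 0.3 SD.

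**Step 1. Standard error used by the t test.**
SE = SD × √(1/50 + 1/121) = SD × √(0.02000 + 0.00826) = 0.168 SD.

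**Step 2. Error rate when technique has no effect but the series differ by b.** By the normal approximation, error = Φ(−1.96 + b/SE) + Φ(−1.96 − b/SE).

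| Shift b (SD) | b/SE | Two terms | Two-sided error |
|---|---|---|---|
| 0 | 0 | 0.025 + 0.025 | 5% |
| 0.1 | 0.595 | 0.086 + 0.005 | 9.1% |
| 0.2 | 1.190 | 0.221 + 0.001 | 22.1% |
| 0.3 | 1.784 | 0.430 + 0.000 | 43.0% |

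The noncentral t with 169 degrees of freedom gives 9.1%, 21.9% and 42.6%. The two-sided figures are the same whichever group the shift favours.

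**Step 3. More patients do not help.** Doubling both groups gives SE = 0.168/√2 = 0.119 SD. For b = 0.2 SD, b/SE = 1.68 and the error is Φ(−0.28) + Φ(−3.64) = 39%, against 22% at the planned sizes. The sampling error shrinks and the shift stays.

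**Step 4. The same in UPDRS part 3 points, for a range of assumed SDs.**

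| Assumed SD (points) | SE (points) | Error, 1-point shift | 2 points | 3 points |
|---|---|---|---|---|
| 8 | 1.34 | 12% | 32% | 61% |
| 10 | 1.68 | 9% | 22% | 43% |
| 12 | 2.02 | 8% | 17% | 32% |
| 14 | 2.35 | 7% | 14% | 25% |

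**Step 5. What adjustment could do.** With patient-level Group 1 data, adjusting for age, baseline score or target could remove differences that act through those variables. Programme, period and assessment setting would remain, since each is constant within a series or cannot be separated from it.

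**The case against.** The plan discloses its historical control openly, and this criticism applies to any externally controlled study. There is also some protection in the design. The endpoint is within-patient change, so a constant rater offset present at both visits cancels. Inclusion criteria 1a to 1d restrict case mix. The size of the remaining shift is unknown, so every figure above is conditional.

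All of that stands, and it limits how strongly the point can be put. It does not supply the missing allowance. Differences in programming, period, case mix or the way change is scored do not cancel, and disclosing a design is not the same as analysing its consequences.

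A reader might infer four stronger points that the documents do not support:

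- **That the plan's 95% interval is too narrow.** No interval is planned, and a fixed shift moves an interval off-centre without altering its width. An interval is too narrow only under a model of random between-series variation, whose size these two series cannot estimate.
- **That a specific true error rate or interval width can be stated.** This needs both an SD and a between-series variance, and the documents give neither.
- **That separate teams rated the two series.** This is plausible, but the documents do not say who rates in either series, nor do they list the external study's sites.
- **That an in-house MER group should have been required.** Section B says "Throughout the history of DBS implant procedures at OHSU, MER and mapping of target structures has been the gold standard", and E.1 says "All clinical outcome measures are standard of care in the movement disorders center for patients in the deep brain stimulation program". Neither shows that past MER patients at OHSU have OFF-medication UPDRS part 3 scores at both baseline and 6 months. An earlier in-house group would still differ in period, and a concurrent one by patient choice. Exclusion 6 simply defines Group 2.

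**Conclusion.** The concern holds as a matter of confounding and attribution. Technique equals data source for all 171 patients (50 + 121), and the primary test counts patient sampling error only. Its 5% level applies to technique only if the net series difference in mean change is exactly zero.

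The size is illustrative: about 9%, 22% or 43% two-sided error for an assumed fixed shift of 0.1, 0.2 or 0.3 SD. The direction is unknown. Section B says that "OHSU has been a pioneer in the development and use of DBS", from which a reader might infer a shift in favour of Group 2, but the documents give no evidence on its sign or size. This matters most for a non-inferiority claim. A shift favouring Group 2 would make a false claim more likely, and a shift favouring Group 1 would make it less likely.

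The study can proceed, but the plan should show how sensitive its conclusion is to such a shift and limit the claim to match.

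**What to change.** In D(2):

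1. Report the primary difference in mean change with its 95% confidence interval as well as the test.
2. Pre-specify a bias-shift (tipping-point) table that recomputes the difference and interval after adding a series shift of 0, 1, 2 and 3 UPDRS part 3 points in either direction. Label the range as an assumption.
3. State the smallest shift that changes the stated conclusion. For the planned analysis that conclusion is the two-sided test result. If non-inferiority is claimed, it is the conclusion against a margin fixed in advance, without which the tipping point is undefined.
4. Word the conclusion as a comparison with an external series, not as the isolated effect of the placement method.

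**Cost.** One paragraph, one table and a more cautious conclusion. No new data or patients are needed. The table does not remove the confounding; it shows how much of it the conclusion can withstand.

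### Zero change is the only rule for missing primary data; between two active DBS techniques it can bias the contrast in either direction, and no sensitivity analysis is planned

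*Combined protocol and SAP*

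**What the plan says.** Section D(2), Analysis, compares Groups 1 and 2 on change in UPDRS part 3 (off medication, on stimulation) at 6 months, by intent to treat, with a 2-sample t test on mean change. On missing data it says: "For patients without baseline data, follow-up data or both, the change score will be set to zero". It gives no reason for zero, no expected missing rate, no alternative method and no sensitivity analysis, and no other section supplies them.

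Four other places bear on the point.

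- Setting and Subjects, in the opening summary, fixes the study group at implantation: "Enrollment will continue until fifty subjects meeting inclusion and exclusion criteria have been implanted with electrodes".
- Analysis, in the opening summary, intends complete follow-up: "All patients will present for a 6 month visit following electrode placement".
- Section C.1 describes the 121 historical controls in two ways: "The information collected from these patients will be compared to the published data on 121 DBS patients" and "We will obtain de-identified data from the VA Cooperative study". It adds: "No medical records, source documents, or case report forms will need to be accessed to obtain the necessary values".
- The schedule in section C.2 places every outcome scale at baseline and at 6 months only. The 30-, 60- and 90-day visits carry none.

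**The concern.** Here both groups have electrodes implanted and stimulated, so zero is not a neutral value. Each zero pulls its own group's mean towards no benefit from DBS. How hard it pulls depends on how many patients are missing and how well they actually did.

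The comparator is historical. Completeness of follow-up therefore comes from two separate studies, and nothing in the design balances it. In Group 2, a patient lost after implantation stays in the intent-to-treat set as a zero.

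The background section hypothesises comparable outcomes, and section E.2 hopes to show non-inferiority. A rule that can shrink, exaggerate or create a difference matters for that aim, and as written the reader cannot tell which is happening.

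**Working it through.** **Inputs.** From the documents: 121 controls (Group 1) and 50 new-technique patients (Group 2), a 2-sample t test, two-sided 0.05. The documents give no mean change, SD or missing rate, so there is no figure of the plan's own to reproduce. Assumed: mean improvement 12 points, SD 8 to 14, and missing fractions of 0 to 10%. Missingness is written control/new, and improvement counts as positive.

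**Bias formula.** Setting a missing patient's change to zero lowers the group mean by m*d. For new minus control:

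bias = m1*d1 - m2*d2.

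It is zero only if the two terms cancel, which includes the case where the missing patients truly did not change. With d = 12, one missing Group 2 patient lowers that mean by 12/50 = 0.24 points. One missing Group 1 patient lowers that mean by 12/121 = 0.10.

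**No true difference (12 v 12), missingness unrelated to outcome.** Rejection rates come from simulation: 100,000 runs, normal changes, pooled t test, Monte Carlo error at most 0.2 percentage points.

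| Missing | Bias | SD 8 | SD 12 | SD 14 |
|---|---|---|---|---|
| 5%/0% | 0.05*12 = +0.6 | 6.9% | 5.9% | 5.8% |
| 0%/5% | -0.6 | 7.6% | 6.1% | 5.6% |
| 10%/0% | 0.10*12 = +1.2 | 13.4% | 9.2% | 8.3% |
| 0%/10% | -1.2 | 14.7% | 9.3% | 7.8% |

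At 10%/10% and SD 12 the bias is 0 and rejection is 5.0%. At 10%/0% and SD 12, 8.7 of the 9.2 percentage points are false advantages for the new technique.

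**True deficit of 4 (12 v 8), SD 12, missingness unrelated to outcome.** The expected difference is (1-m2)*8 - (1-m1)*12.

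| Missing | Expected deficit | Chance of detecting it |
|---|---|---|
| none | 4.0 | 51% |
| 5%/5% | 3.8 | 47% |
| 10%/10% | 3.6 | 44% |
| 5%/0% | 3.4 | 39% |
| 0%/5% | 4.4 | 59% |
| 10%/0% | 2.8 | 28% |
| 0%/10% | 4.8 | 67% |

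With equal missingness the deficit shrinks by (1-m): 0.9*4 = 3.6 at 10%.

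**Would multiple imputation alone cure it?** Take 10%/10%, completers improving by 12 in both groups, missing controls also improving by 12 (d1 = 12), and missing Group 2 patients who lost all benefit (d2 = 0).

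- Truth: (0.9*12 + 0.1*0) - 12 = -1.2.
- Zero rule: 0.9*12 - 0.9*12 = 0, an error of +1.2.
- Missing-at-random imputation, when the imputation variables do not predict the loss of benefit: 12 - 12 = 0, the same error of +1.2.

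The two methods agree and both are wrong. With d1 = 0 and d2 = 12 the truth is +1.2, both again give 0, and the error is -1.2. An analysis that varies d1 and d2 separately covers these cases:

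[(1-m2)*12 + m2*d2] - [(1-m1)*12 + m1*d1].

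**The case against.** The strongest reply is that little may be missing. A 6-month visit is planned for every patient, section E.1 calls the outcome measures standard of care, and patients are examined before surgery, so missing baselines should be few. At a 5-point gap the bias is only 0.6 points. The larger figures need something like 12 of 121 controls missing and none of 50. All of this stands as a limit on size. It does not cover Group 1, whose completeness the documents do not describe.

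A second reply is that zero may match the rule behind the published control values. That would be a fair reason to use it, but the plan does not say so. A shared rule also leaves the bias in place when missing rates differ.

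A third is that imputation is no clean replacement. That is right: with no outcome scale between baseline and 6 months, it would rest mainly on baseline values and a missing-at-random assumption.

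Three stronger readings are tempting.

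- A reader might infer that the rule tilts the study towards non-inferiority. Higher Group 1 missingness, or equal missingness with a true deficit, does favour that conclusion. With similar improvement among the missing, higher Group 2 missingness works against it. The documents do not show which applies.
- A reader might infer that zero is simply conservative. The same figures rule that out as a general claim.
- A reader might infer that the secondary outcomes have no missing-data rule. The zero-change sentence follows the primary outcome, but it sits in the same Analysis section and is not expressly limited to that outcome. This is at most missing detail.

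**Conclusion.** The concern holds in this form: zero change is the sole stated handling of missing primary data, it is not neutral between two active techniques, and nothing in the plan tests how far the result depends on it. The mechanism is certain. The material impact is not, because every missing rate, mean and SD above is assumed.

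On those assumptions, equal missingness unrelated to outcome is mild, a 5-point gap is small, and a 10-point gap is enough to matter: 1.2 points, with false-positive rates of 8-15%. It should be fixed, since the remedy is cheap. The documents do not support saying that the primary result will be wrong, or wrong in a known direction.

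**What to change.** In section D(2):

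1. Use one missing-data rule in both groups, and state whether Group 1 is patient-level data or published summaries, because the next steps depend on it.
2. If Group 1 is patient-level, keep the 2-sample comparison but multiply impute missing baseline or 6-month scores within each group, with the same model and variables, and combine by Rubin's rules. Keep zero change in both groups as a sensitivity analysis. State that imputation rests mainly on baseline values and on missing at random.
3. Add a delta-adjusted (tipping-point) analysis that varies the assumed change of the missing patients separately in each group.
4. If only Group 1 summaries exist, establish the rule behind them before analysing Group 2 and apply it to Group 2 for the contrast. Show the imputed and delta-adjusted Group 2 results alongside, and state that bias from unequal missingness may remain.
5. Report missing counts and reasons by group.

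The cost is SAP wording, some programming and reliance on stated imputation assumptions. If only summaries based on zero change exist, the main contrast is unchanged and the gain is the sensitivity range.
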